## REVISION HISTORY

Revision #	Version Date	Summary of Changes	Consent Change?
1	11/07/2017	

• If subject consents to genetic portion of study, a portion of the baseline blood sample will be used to see if subject has variations of specific polymorphisms that are known to affect drug metabolism.

	Yes - Added to consent form dated 11/07/2017
2	11/17/2017	

• Added a +/- 7 day visit window to add to flexibility for subject scheduling.

• Updated the name of the research team from TRO to SurgCTO.

• Removed the Revised Token Test from the list of assessments to be completed at study visits.

• Removed sentence stating subjects may be approached with study specific information pre-transplant. Subjects may still be told pre-transplant that they may be approached for studies post-transplant.

• Removed Prograf from the protocol and left the immediate-release as a general term because the subjects may be on a generic formulation instead of a brand name formulation

	No
3	05/01/2018	

• Subjects may now complete pre-baseline visit up to 12 months post-transplant

• Updated study visits to accommodate the expansion of the enrollment window to 12 months post-transplant

	Yes – Added to consent form dated 05/01/2018
4	06/04/2018	

• Fix wording issue – clarified that BASELINE occurs no more than 60 days AFTER PRE-BASELINE

• Removed “standard of care” wording as this has changed

	Yes – Added to consent form dated 06/04/2018

PROTOCOL TITLE: CMET  
VERSION DATE: 09/06/2019

		since the previous version	
5	07/31/2018	Added information into section 18.0 of the protocol.	Yes – consent form dated 07/31/2018
6	09/11/2018	

Subjects may now complete pre-baseline visit up to 36 months post-transplant

Updated study visits to accommodate the expansion of the enrollment window to 36 months post-transplant

	
7	09/06/2019	

Increase age range to “18 and above”

Eliminate study visit (#5) at 24-weeks post baseline, which lowers total compensation to \$200 and shortens total study duration

	Yes – consent form dates 09/06/2019

## **ABBREVIATIONS/DEFINITIONS**

- COWA: Controlled Oral Word Association
- Immediate Release: IR
- Extended Release: XR

## STUDY SUMMARY

Study Title	Comparison of the cognitive and motor effects of treatment between an immediate- and extended-release tacrolimus ( Envarsus® XR ) based immunosuppression regimen in kidney transplant recipients
Study Design	Between four (4) and 38 months after receiving a kidney transplant and having been placed on an immediate-release (IR) tacrolimus immunosuppressant regimen, participants in this study will undergo cognitive and motor function testing and have a blood sample collected (BASELINE). Half of the participants will then be randomly converted to extended-release (XR) tacrolimus ( Envarsus® XR ) while the other half will remain on IR tacrolimus for the duration of the study. Both the IR and XR groups will repeat the cognitive and motor function testing and have a blood sample collected at 6 and 12 weeks Post-BASELINE. A practice version of the cognitive and motor function tests will be administered no more than 60 days before the baseline visit (Pre-BASELINE). Alternate versions of the cognitive and motor tests will be used at each Post-BASELINE testing session to control for possible practice effects.
Primary Objective	The primary objective is to compare the effect of treatment with an immediate-release tacrolimus to an extended-release tacrolimus (i.e., Envarsus® XR ) immunosuppressive regimen on cognitive and motor function in kidney transplant recipients.
Secondary Objective(s)	The secondary objective is to determine the factors that explain inter-individual variability in cognitive response. Pharmacokinetic and demographic factors will be explored. Variability in cognitive response between individuals can be large. A population approach (nonlinear, mixed effects ) will be used. Measurement of drug concentration will be the dependent variable.
Research Intervention(s)/Investigational Agents	Immunosuppressant tacrolimus immediate release (IR) and extended release (XR) formulation ( Envarsus® XR )
IND/IDE # (if applicable)	Exempt
Study Population	Male and non-pregnant female kidney transplant recipients ages 18 and above.
Sample Size (number of participants)	We expect to enroll 74 patients to achieve 65 completers.
Study Duration for Individual	Six months (including pre-baseline testing)

PROTOCOL TITLE: CMET  
VERSION DATE: 09/06/2019

Participants	
---------------------	--

## 1.0 Objectives

**1.1** Purpose: The purpose of this study is to demonstrate whether or not the extended-release tacrolimus, namely, Envarsus XR, produces fewer adverse cognitive and motor effects than the commonly used immediate-release tacrolimus formulation in kidney transplant recipients.

## 2.0 Background.

**2.1 Significance of Research Question/Purpose:** The calcineurin inhibitor (CNI) tacrolimus is one of the most frequently used immunosuppressants in kidney transplantation, both in early posttransplantation and as part of long-term maintenance regimens (Barraclough et al, 2011. Rostaing et al, 2016). Yet, like other CNIs, such as cyclosporine, tacrolimus is associated with numerous adverse effects including neurotoxicity, which affects approximately 10-28% of patients (Bechstein, 2000). Yet, CNI-related neurotoxicity is not well characterized, and is generally diagnosed using subjective criteria around clinical symptoms rather than objective assessments, complicating the determination of its true incidence. Typically, tacrolimus-associated neurotoxicities present as cognitive impairment, including memory deficits, tremors, altered mental status, confusion, headaches, hallucinations and/or ataxia (Cheng et al, 2012; DiMartini et al 2008), any one of which can result in a substantial reduction in the recipient's quality of life and negatively affect medication adherence. Moreover, the pathogenesis of CNI-related neurotoxicity is unclear and confounded and/or exacerbated by the presence of comorbid conditions, such as increasing age, hypomagnesemia (Thompson et al, 1984), and hypertension (Bechstein, 2000).

The cellular mechanisms underlying the adverse neurologic effects associated with tacrolimus have not been conclusively established. Tacrolimus may modulate the activity of both excitatory (NMDA) and inhibitory (GABA) amino acid receptors via calcineurin. In turn, calcineurin may modulate glutamatergic neurotransmission pre- and postsynaptically (Sander et al, 1996) as well as regulate desensitization of GABA receptors (Martina et al, 1996). Tacrolimus also inhibits the induction of long-term potentiation, which can interfere with memory acquisition (Bechstein, 2000). There is also evidence that tacrolimus causes selective toxicity of glial cells (Stoltenburg-Didinger & Boegner, 1992) and induction of apoptosis of oligodendrocytes (McDonald et al, 1996) though it not known what role these mechanisms play in the clinical manifestation of tacrolimus-related neurotoxic effects.

The lack of precise characterization of the neurotoxicities, specifically, the cognitive and motor dysfunctions associated with tacrolimus administration, as well as the gaps in our understanding of their pathogenesis severely limit the clinician's ability to reduce or prevent their occurrence. Current strategies aimed at managing these adverse events are based on the assumption that most of the symptoms are dose-related and only occur at elevated and/or peak serum tacrolimus levels blood levels (Ayres et al, 1994; Guarino et al, 1996; Bechstein, 2000; Rostaing et al, 2016). In addition, the symptoms of tacrolimus-associated neurotoxicity may be reversed in most patients by substantially reducing the dosage of immunosuppressant (Bechstein, 2000).

**2.2 Preliminary Data:** This study will, for the first time, compare cognitive and motor function in individuals placed on either an immediate- or an extended release formulation of a tacrolimus (*Envarsus® XR*) based immunosuppressive regimen, after receiving a kidney transplant. In addition to subjective measures such as the NIH PROMIS scales and the SF-12, objective assessments not previously used in the renal transplant population will be administered in order to more precisely characterize drug related cognitive and motor impairments.

**2.3 Existing Literature:** The widely used immediate-release, twice-daily capsule formulation of tacrolimus, while highly effective in preventing acute transplant rejection, has severe limitations, such as a narrow therapeutic window, interindividual variation in absorption, and low bioavailability (17% +/- 10%). *Envarsus® XR* (Veloxis Pharmaceuticals), an extended-release, once daily, tablet formulation, was developed using a proprietary drug delivery technology that critically affects drug dissolution and absorption. Consequently, *Envarsus® XR* shows a more consistent concentration-time profile over 24 hours, with reduced peak and peak-to-trough fluctuations, when compared to immediate-release tacrolimus (Rostaing et al, 2016) in de novo and stable kidney recipients similar to those participating in this study (Rostaing et al, 2016). Moreover, patients converted from immediate-release formulations to *Envarsus® XR* initially receive only 80% of prior immediate-release dosage orally once daily (Bunnapradist et al, 2013; Rostaing 2017). Therefore, compared to immediate-release tacrolimus, the extended-release formulation, *Envarsus® XR*, when taken once-daily, slows drug absorption and delivers more constant plasma concentrations with less frequent dosing, thereby potentially mitigating neurotoxic events associated with high peak drug concentrations.

Our central hypothesis is that kidney transplant recipients, when placed on a regimen of *Envarsus® XR* q.d., will experience significantly fewer adverse cognitive and motor side effects than when on a regimen of immediate release tacrolimus b.i.d.

### **3.0 Study Endpoints/Events/Outcomes**

**3.1 Primary Endpoint/Event/Outcome:** The primary objective is to compare the effect of treatment with an immediate-release tacrolimus to an extended-release tacrolimus (*Envarsus® XR*) immunosuppressive regimen on cognitive and motor function in kidney transplant recipients. Our primary outcome measure is the Controlled Oral Word Association (COWA: phonemic generative fluency). COWA was chosen as the primary endpoint since in previous head-to-head studies of drug-induced cognitive impairment, this measure was sensitive to the differential effects of the study drugs (Medor et al, 2003; Marino et al, 2012) including patients on calcineurin inhibitors (Syrjala et al, 2004). The primary endpoint is a change in the COWA score from baseline to each post-transplant assessment).

**3.2 Secondary Endpoint(s)/Event(s)/Outcome(s):** The secondary objective is to determine the factors that explain inter-individual variability in cognitive

response. Pharmacokinetic and demographic factors will be explored. Variability in cognitive response between individuals can be large. A population approach (nonlinear, mixed effects) will be used. Measurement of drug concentration will be the dependent variable.

#### **4.0 Study Intervention(s)/Investigational Agent(s)**

**4.1** Description: The cognitive and motor effects of two FDA-approved formulations of the immunosuppressant drug tacrolimus (on-label use for kidney transplant recipients) will be evaluated: an immediate-release formulation and the extended-release formulation, Envarsus®XR.

**4.2 Drug/Device Handling:** Immediate-release tacrolimus will be prescribed by the treating physician and dispensed by the patient's pharmacy of choice. Envarsus®XR will be supplied by the sponsor, namely, Veloxis Pharmaceuticals and shipped to the Investigational Drug Services (IDS), Pharmaceutical Service, Fairview-University Medical Center, who will dispense it to patients in the XR group as prescribed by the treating physician (on-label use). Upon receipt of the study treatment supplies, the IDS staff will perform an inventory and a drug receipt log filled out and signed by the person accepting the shipment. The designated study staff will count and verify that the shipment contains all the items noted in the shipment inventory. Any damaged or unusable study drug in a given shipment will be documented in the study files. The study drug will be stored according to the stated FDA requirements as outlined in the "Storing Investigation Study Drugs" SOP dated 07/23/2003.

Regular study drug reconciliation will be performed by the study team to document drug assigned, drug consumed, and drug remaining. This reconciliation will be logged on the drug reconciliation form, and signed and dated by the study team.

At the completion of the study, there will be a final reconciliation of drug shipped, drug consumed, and drug remaining. This reconciliation will be logged on the drug reconciliation form, signed and dated. Any discrepancies noted will be investigated, resolved, and documented prior to return or destruction of unused study drug. Drug destroyed on site will be documented in the study files.

#### **4.3 IND/IDE: EXEMPT.**

#### **5.0 Procedures Involved**

Study Design: All subjects will undergo cognitive and motor function testing no earlier than two (2) months post-transplant and no later than 36 months post-transplant to become familiar with the test battery (Pre-BASELINE). The Pre-BASELINE session will take place no more than 60 days prior to the BASELINE visit. Between four (4) and 38 months post-transplant, subjects will have one blood sample taken, after which they will be administered the full battery of cognitive and motor function tests as well as self-report measures of health-related quality of life.

**5.1** (Baseline). Subjects will then be randomized to remain on immediate-release tacrolimus (IR group) or switched to Envarsus XR (XR group). Both groups will have one, approximately 10-mL blood sample collected and be

administered the cognitive, motor function, and self-assessments at 6 and 12 weeks after BASELINE..

### 5.2 Study Procedures:

Patients participating in this study are placed on immediate-release tacrolimus immediately following transplant. Four (4) to 38 months post- transplant, half of the patients will be randomly chosen to convert to Envarsus XR, while the other half will remain on immediate release tacrolimus. Both the IR and XR formulations of tacrolimus have been approved by the FDA for use as an immunosuppressant in kidney transplant recipients and will be prescribed/dosed by the treating physician as FDA indicated.

Patients in both the IR group and the XR group will undergo cognitive and motor function testing at the following times: (1) at least Two (2) - three (3) months post-transplant (maximum 36 months post-transplant): pre-BASELINE; (2) Four (4) to 38 months post-transplant: BASELINE; (3) 6-weeks Post- BASELINE; (4) 12-weeks Post-BASELINE. Since patients on either IR or XR require therapeutic drug monitoring as part of their SOC, the blood sample taken BASELINE and at 6 and 12 weeks post-BASELINE may coincide with blood levels taken as SOC. Each visit will include a +/- seven (7) day window to increase flexibility for the subject's schedule. At each visit, subjects will be administered the following:

*Executive function, processing speed, and word-level language/verbal tests:*

- Phonemic generative verbal fluency will be evaluated using the COWA test. COWA requires the subject to generate words other than proper names or numbers beginning with a specific letter of the alphabet; three 60-second trials are obtained, using three different letters, usually F-A-S or B-H-R. *This is a primary Outcome Measure.*
- Symbol Digit Modalities Test (SDMT) is a test of psychomotor speed that requires the subject to transcribe symbols to numbers as quickly as possible with a combination of direct visual identification and short-term memorization. Symbols with empty squares are presented and the task is to fill in the corresponding number as quickly as possible. This task is timed at 90 seconds. *This is a primary Outcome Measure.*
- Semantic generative verbal fluency will be evaluated using the Animal Fluency test. Subjects are asked to generate as many different animal exemplars as they can within 60 seconds. The primary dependent measure for both phonemic and semantic generative fluency is the number of correct words meeting scoring criteria normalized to individual (averaged) baseline.
- Trails A and B will be used to assess visual search, mental flexibility, and task alternation. The subject is required to draw lines between circles in ascending order (“connect the dots”). Trail Making Part A requires the patient to connect the numbers from 1-25. Trail Making B requires subjects to alternate between numbered and lettered circles in ascending numerical/alphabetical order (e.g., 1-A-2-B, etc.) The primary dependent measure is time of completion.
- Digit span subtest from the WAIS-IV will be used to assess immediate attention. It tests forward and backward digit span, includes a sequencing trial in which the subject is the repeat back the digits in ascending order.

*Computerized psycholinguistic assessment:*

- Spontaneous narrative (SN) task presents the subject with an interpersonal conflict scenario (e.g., “a relative in the nursing home that is being mistreated”) and is asked to explain how he/she would address the conflict in a three (3) minute speech. Different but equivalent scenarios will be used for the different study sessions to minimize practice effect.
- Picture Description task requires the subjects to describe a simple picture (e.g., The “Cookie Theft” stimulus from the Boston Diagnostic Aphasia Examination (Goodglass & Kaplan 1983).

Linguistic analysis of speech and language functioning will be performed on speech samples recorded during discourse level language/verbal tests. Both what the subjects said (*content*) and how they said it (*manner*) in response to a task such as story recall or spontaneous narrative task will be analyzed.

*Motor Assessments*

- Tremor will be assessed as follows: Study staff will videotape the subject while the subject performs tasks such as sitting with hands and feet relaxed, extending the arms outstretched, pointing with the fingers, pointing with the feet, pouring water (with the hands), drawing lines and spirals (with the hands), writing (with the dominant hand), holding the head upright, extending the tongue. The videos and the drawing / writing samples will be coded to ensure blinding, then rated according to the Fahn Tolosa Marin scale (Fahn et al, 1988) by a blinded rater. Videos will be stored on a University-approved encrypted server.
- Manipulative dexterity/fine motor coordination will be assessed using Grooved Pegboard Test, which involves placing 25 pegs as rapidly as possible into an equivalent number of similarly shaped holes, but varying in their orientation to the vertical. The primary dependent measure is the time it takes to complete the task.

*Quality of Life Assessment*

- Self-report measures of health-related quality of life will either be completed online using the brief, but highly reliable computer adapted tests of the NIH PROMIS system. [[www.NIHpromis.org](http://www.NIHpromis.org)] or static short forms by pencil and paper. PROMIS scales will include: Physical Health (Physical function, pain intensity, pain interference, fatigue, sleep disturbance, sleep-related impairment); Mental Health (depression, anxiety); Social Health (satisfaction with social roles). These measures, along with the SF-12, will be administered at the times of the cognitive assessment and will take 15 minutes or less to complete.

*Blood Draw*

- One 7 to 10 mL blood sample will be collected at each visit. Over the course of the study, we will collect about 6 to 9 teaspoons of blood.
- If the subject consents to the genetic portion of the study, a portion of the baseline blood draw will be used to study specific polymorphisms that are known to affect how tacrolimus metabolizes in the body. The subject may still participate in study even if they do not consent to the genetic option.

**5.3** Follow-Up: After the last study session at 12 weeks Post-BASELINE, patients who were assigned to the *Envarsus® XR* group will have the opportunity to remain on the extended-release formulation at their own expense.

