## 11.0 Local Number of Participants

**11.1** Local Number of Participants to be Consented: Sample size is based on the primary endpoint (COWA). In a longitudinal neurocognitive study of patient on immune suppressant drug therapy Syrjala et al (2004) found that the mean T score for the COWA (based on a population norm set at 50, with a standard deviation SD of  $\pm 10$ ) declined by 5 units (0.5SD) from pretransplantation to 80 days posttransplantation. Since a change of 0.5SD is considered standard clinical criteria for a medium effect size, we based our calculation of the power for the COWA upon a standard deviation of the difference score between baseline and follow up of a 5-point performance decline. Therefore, a total of 65 patients will yield a probability of 80 percent that the proposed study will detect a treatment difference of 5 units in COWA at a two-sided 0.05 significance level. To account for possible dropouts, we will recruit 74 patients.

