PK/PD Modeling: A pharmacokinetic (PK) pharmacodynamics (PD) approach can give insight in understanding how the body influences tacrolimus concentrations (PK step) and how variations of these concentrations influence neurocognitive performance (PD step). Single trough levels will be obtained at study visits, which in some instances may overlap with routine clinical care. Sparse sampling requires a non-linear mixed effects approach (i.e., NONMEM) that is robust with respect to missing data and sparse data sets. Covariates known to effect drug disposition in this population such as age, renal function, gender, co-medications, etc. will be included in the model building algorithms. These data will be collected from the patient medical record. PD modeling will investigate if a relationship exists between clinical covariates associated with the cognitive and motor measures (such as COWA) and drug concentration and derived measures of drug exposure.

**16.2 Power Analysis:** Sample sized is based on the primary endpoint (COWA). In a longitudinal neurocognitive study of patient on immune suppressant drug therapy Syrjala et al (2004) found that the mean T score for the COWA (based on a population norm set at 50, with a standard deviation SD of  $\pm 10$ ) declined by 5 units (0.5SD) from pretransplantation to 80 days posttransplantation. Since a change of 0.5SD is considered standard clinical criteria for a medium effect size, we based our calculation of the power for the COWA upon a standard deviation of the difference score between

baseline and follow up of a 5-point performance decline. Therefore, a total of 65 patients will yield a probability of 80 percent that the proposed study will detect a treatment difference of 5 units in COWA at a two-sided 0.05 significance level. To account for possible dropouts, we will recruit 74 patients.

**16.3 Data Integrity:** Data will be stored in REDCap, a database secured by the University of Minnesota. All data will be double entered by trained study staff. Specimens will be stored in the -80 freezer in lab 522C, [name]. Data and specimen will be kept until the completion and publication of final manuscripts. Primary investigators and study staff with proper training will have access to the data and specimens. Video (i.e., tremor assessments) and audio (cognitive testing/language) recordings will be stored on a University of Minnesota/HIPAA-approved encrypted server.

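### The primary COWA outcome is a change from baseline in section 3.1 but a word count normalised to an undefined averaged baseline in section 5.2, and its scale is never stated

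*Combined protocol and SAP*

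**What the plan says.** Section 3.1 names COWA as the primary outcome and states: "The primary endpoint is a change in the COWA score from baseline to each post-transplant assessment". Section 5.2 labels COWA a primary outcome measure. Two bullets later, in a sentence covering both fluency tests, it gives the main measure as "the number of correct words meeting scoring criteria normalized to individual (averaged) baseline".

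The schedule in sections 5.0 to 5.2 has one BASELINE visit before randomisation. The only earlier score is Pre-BASELINE, at most 60 days before, which the study summary describes as a practice version and section 5.0 as a way to become familiar with the battery.

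Sections 11.1 and 16.2 take the planning effect from "the mean T score for the COWA (based on a population norm set at 50, with a standard deviation SD of" 10), then claim power to "detect a treatment difference of 5 units in COWA at a two-sided 0.05 significance level", without naming a scale in that sentence. Section 16.1 plans repeated-measures ANOVA and change-score summaries. It also uses a 4-point decline as the individual threshold for verbal fluency, again with no scale.

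**The concern.** COWA is the phonemic test, so the section 5.2 sentence applies to the primary outcome and does not match section 3.1. Three matters are left open:

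- **Operation:** subtract the baseline or divide by it.
- **Baseline:** the single BASELINE score, or an average that could only include the practice session.
- **Scale:** raw words or T score.

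The first two alone give four candidate primary variables. Section 16.1 says that a single primary measure was chosen to keep control of the type I error rate. That purpose is weakened if the variable can be settled after the data are seen. The sample size cannot be checked against the endpoint either, because the SD it needs belongs to a variable that is not fixed.

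**Working it through.** **1. The plan's own figure.** Inputs from sections 11.1 and 16.2: difference 5, two-sided 0.05, 80% power, 65 completers. Section 5.2 gives equal allocation ("half of the patients will be randomly chosen to convert to Envarsus XR"). For two parallel groups, n per arm = 2 × (1.960 + 0.842)² × SD² / 5² = 15.70 × SD² / 25.

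- SD 5, the literal reading of "a standard deviation of the difference score between baseline and follow up of a 5-point performance decline": 15.7, so 16 per arm and 32 in total.
- SD 10, the T-score norm: 62.8, so 63 per arm and 126 in total.
- Solving for 65: SD = 5 × √(32.5 / 15.70) = 7.19, or about 7.07 by the t-test with 32 versus 33.

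Neither SD in the text gives 65. If the SD at each visit is 10, the SD of change is 10√(2(1 − r)), so 7.07 to 7.19 means r of about 0.75 to 0.74. No retest correlation r is stated. The range below is therefore an assumption.

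**2. Power by definition.** SD 10 at each visit, difference 5, 32 versus 33, two-sample t-test, and equal correlation r among Pre-BASELINE, BASELINE and follow-up:

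| Definition | SD formula | r = 0.60 | r = 0.75 | r = 0.85 |
|---|---|---|---|---|
| Change from BASELINE | 10√(2(1 − r)) | 8.94: 60% | 7.07: 80% | 5.48: 95% |
| Change from two-visit average | 10√(1 + (1 + r)/2 − 2r) | 7.75: 73% | 6.12: 90% | 4.74: 99% |
| ANCOVA on BASELINE alone | 10√(1 − r²) | 8.00: 70% | 6.61: 85% | 5.27: 97% |

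**3. Ratio readings.** These need an assumed mean and SD and were simulated at r = 0.75 with an effect of 0.5 SD. Over the T scale and plausible word counts, power is about 56 to 74% for a ratio to BASELINE and 78 to 86% for a ratio to the average. These are rough. Runs of 20,000 trials on the T scale (mean 50, SD 10) and on word counts with means 35 to 40 and SD 10 or 12, taking the effect either as a gain or as a loss, spanned 50 to 79% and 71 to 90%.

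**4. Can the choice change the conclusion?** In simulation with a true effect, change from BASELINE and ratio to the average disagreed on p < 0.05 in about 4 to 22% of trials for r from 0.60 to 0.85. With no effect and r = 0.75, reporting whichever of the four versions was significant raised the false-positive rate from 5% to about 9%.

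**5. Does the practice session help?** Suppose Pre-BASELINE correlates 0.5 with the other visits, while BASELINE and follow-up correlate 0.75.

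- Change from the average: SD = √(100 + 75 − 125) = 7.07, power 80%, no gain over BASELINE alone.
- ANCOVA on the average: SD = √(100 − 62.5²/75) = 6.92, power 82%, against 85% for ANCOVA on BASELINE.
- ANCOVA with the two scores as separate covariates: R² = (0.25 + 0.5625 − 0.375)/0.75 = 0.583, SD = 10√0.417 = 6.45, power 87%.

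**6. Scale.** Under one common linear norm, T score and raw words give the same test. The scale matters when the size of 5 units is interpreted. With an assumed raw SD of 12, 5 words is 50/12 = 4.2 T points. Power then falls from about 81% to about 66% (normal approximation, SD of change 0.7117 × 12 = 8.5).

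**The case against.** Section 3.1 is where the endpoint is defined, and the change-score summaries in section 16.1 agree with it. Section 5.2 describes test scoring and gives a main measure in the same way for Trail Making and the Grooved Pegboard, which are not primary outcomes. Normalising to baseline can mean subtraction, in which case only the choice of baseline differs. This is a fair reading and narrows the gap, but it does not close it: the sentence expressly covers the phonemic test, and the averaged baseline still has no definition in the schedule.

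Four stronger readings might be inferred, and the documents support none of them.

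- **That the T score is a third endpoint definition.** It is the scale of the planning effect. A change from baseline can itself be in T units.
- **That the plan prescribes a ratio, so 5 units and 4 points lose their meaning.** No text says ratio or percentage. The 4-point threshold also belongs to the separate individual-decline analysis.
- **That the section 5.2 measure has less power than claimed.** If it is a ratio, it is to the averaged baseline, and its simulated power falls on both sides of 80%. The lowest figures are for a ratio to a single baseline, which no section defines.
- **That averaging in Pre-BASELINE is a free gain.** Step 5 shows that this depends on how well a practice session correlates with later scores.

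It is also true that the missing SD matters more for power than the definition does. By t-test, 65 patients have about 51% power at SD 10 and 98% at SD 5. The correlation of 0.75 is only back-solved. A paired calculation with SD of difference 14.14 also gives 64.7, rounded to 65, although that is not this design.

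**Conclusion.** The concern holds as a contradiction in the primary outcome: sections 3.1 and 5.2 give different measures, no section reconciles them, and the averaged baseline and the scale are undefined. Over the assumed correlations, moving from a single to an averaged baseline changes power by about 4 to 13 points (73 − 60 at r = 0.60; 99 − 95 at 0.85). Ratio readings add further spread. The size rests on SD 10 at each visit, an assumed r and, for the averaged baseline, equal correlation of the practice session. The documents supply neither r nor a clear SD of change, so no single power loss or gain can be claimed. That the variable is undefined does not depend on these assumptions.

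**What to change.** Delete the normalising and averaging phrase from section 5.2. Use one definition in sections 3.1, 5.2, 11.1, 16.1 and 16.2: COWA score on the absolute scale with no ratio, the scale named (raw words, or T score with the norm identified), at the post-baseline visits already scheduled at 6 and 12 weeks. Compare arms by ANCOVA or a mixed model with the BASELINE COWA score as covariate. Pre-BASELINE may enter as a separate covariate but should not be forced into an average. State the scale of the 4-point decline. Then restate the power for the parallel design with an explicit SD for that variable and its source.

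The cost is wording and a slightly different model, using scores already collected. On the assumptions in step 2, ANCOVA on BASELINE has more power than change from the same baseline. The change should be made before outcome data are compared by arm.
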